### 3.3 Patient enrolment

The Principal Investigator (PI) or designee will:

1. Obtain signed informed consent from the potential patient before any study-specific procedures are performed.
2. Assign potential patient a unique enrolment code (E-code) beginning with 'E#' after written informed consent has been obtained. The E-code (EWWXXYZZ) will consist of a 2-digit country number (WW), a 2-digit site number (XX), a 1-digit study number (Y) and a 2-digit patient number (ZZ, starting with 01) issued by the study centre in order of informed consent taken.
3. Determine patient eligibility. See Sections 3.1 and 3.2.

If a patient withdraws from participation in the study, then his/her enrolment/randomisation code cannot be reused.

Patients who were enrolled, screened but not dosed (ie, withdrew from the study prior to dosing) may be re-enrolled and re-screened if, in the opinion of the Investigator, the reason(s) for earlier withdrawal no longer applies. Patients cannot re-enter the study if dosed and subsequently withdrawn from the study. Patients who discontinue their participation in the PK phase prematurely may still be eligible to continue to take osimertinib in continued access, if the Investigator believes it is in the patient's interest, ie, discontinuation from the PK phase may not necessarily result in withdrawal from the study.

### 3.4 Procedures for handling incorrectly enrolled patients

**Patients who fail to meet the eligibility criteria should not, under any circumstances, be enrolled or receive study drug. There can be no exceptions to this rule.**

Where patients who do not meet the selection criteria are enrolled in error or incorrectly started on treatment, or where patients subsequently fail to meet the study criteria post-initiation, a discussion should occur between the AstraZeneca Physician or his/her representative and the Investigator regarding whether to continue or discontinue the patient from treatment. Once a decision is made, Investigators need to ensure they comply with all applicable requirements for human patient protection and ethical review.

The AstraZeneca Physician or his/her representative is to ensure all such decisions are appropriately documented. In situations where an agreement cannot be reached, the patient should have their study treatment stopped and be withdrawn from the study.

### **3.5 Methods for assigning treatment groups (Not applicable)**

### **3.6 Methods for ensuring blinding (Not applicable)**

### **3.7 Methods for unblinding (Not applicable)**

### **3.8 Restrictions**

The following restrictions apply while the patient is receiving study treatment and for the specified times before and after:

1. Females of child-bearing potential should use reliable methods of contraception from the time of screening until 3 months after discontinuing study treatment. Acceptable methods of contraception include “true” abstinence (definition of “true” is when this is in line with the preferred and usual lifestyle of the subject [periodic abstinence, eg, calendar, ovulation, symptothermal, post-ovulation methods and withdrawal are not acceptable methods of contraception]), tubal ligation, oral or transdermal contraceptives, copper-banded intra-uterine devices and vasectomised partner. All hormonal methods of contraception should be used in combination with the use of a condom by their male sexual partner for intercourse. A reduction in the effectiveness of hormonal contraceptives cannot be excluded.
2. Male patients should be asked to use barrier contraceptives (ie, by use of condoms) during intercourse with all partners during the study and for a washout period of 6 months. Where a sexual partner of a male patient is a woman of child-bearing potential, patients should avoid procreation for 6 months after completion of study treatment. Patients should refrain from donating sperm from the start of dosing until 6 months after discontinuing study treatment. If male patients wish to father children they should be advised to arrange for freezing of sperm samples prior to the start of study treatment.
3. All patients must try to avoid concomitant use of medications, herbal supplements and/or ingestion of foods with known potent inducer effects on CYP3A4 and/or known inducer/inhibitor of P-gp (see [Appendix G](#)) whenever feasible, but patients may receive any medication that is clinically indicated for treatment of AEs during the study. Such drugs must have been discontinued for an appropriate period before they enter screening and for a period of 3 months after the last dose of osimertinib. All concomitant medications should be captured on the electronic case report form (eCRF). Guidance on medicines to avoid, medications that require close monitoring and on washout periods is provided in [Appendix G](#).
4. Patients who wear contact lenses must discontinue wearing their lenses if they have any mild to moderate eye symptoms (CTCAE Grade  $\leq 2$ ) while receiving treatment with osimertinib until at least one week after symptoms have resolved. If a patient has a recurrence of eye symptoms or experiences any severe (CTCAE Grade  $\geq 3$ ) ocular events they must discontinue wearing their contact lenses until at least one week after treatment with osimertinib is permanently discontinued. Patients must

not use any eye drops or ointment for treatment of eye symptoms, unless agreed by a study doctor, at any time during the study until 1 week after osimertinib has been permanently discontinued. Patient should consult the clinic promptly if they have any concerns.

5. Patients should maintain a consistent diet during the PK phase of the study and should not change their diet between study periods.
6. On the days of fexofenadine administration, patients must abstain from taking any aluminium and magnesium containing antacids and any other metal containing drugs or products.
7. Patients are not to consume grapefruit, grapefruit juice, Seville oranges, Seville orange marmalade, or other products containing grapefruit or Seville oranges within 7 days of the first administration of the IP through the final PK sample on Day 42 of the PK phase.
8. On fexofenadine dosing days (ie, Day 1 of Treatment Period 1, Day 1 and Day 39 of Treatment Period 2), patients must fast from 1 hour before until 1 hour after dose administration.

Details of restrictions related to concomitant medications can be found in Section [7.7](#).

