### 3.1 Inclusion criteria

For inclusion in the study patients should fulfil the following criteria:

1. Provision of signed and dated, written informed consent prior to any study specific procedures, sampling and analyses. Procedures performed for routine clinical practice up to 2 weeks before the provision of written consent are acceptable if not intentionally done for study purposes.
2. Male or female, aged  $\geq 18$  years
3. Histological or cytological confirmation diagnosis of NSCLC
4. Radiological documentation of disease progression while receiving previous continuous treatment with an EGFR-TKI eg, afatinib, gefitinib or erlotinib. In addition, other lines of therapy may have been given. All patients must have documented radiological progression on the last treatment administered prior to enrolling in the study.
5. Confirmation that the tumour harbours an EGFR mutation known to be associated with EGFR-TKI sensitivity (eg, G719X, exon 19 deletion, L858R, L861Q).
6. Eastern Cooperative Oncology Group (ECOG) performance status 0 to 1, with no deterioration over the previous 2 weeks.
7. Patients must have a life expectancy of  $\geq 12$  weeks, as estimated at the time of screening.
8. Females should be using adequate contraceptive measures (see [Appendix E](#)) and must have a negative serum pregnancy test prior to start of dosing if of child-bearing potential or must have evidence of non-child bearing potential by fulfilling one of the following criteria at screening (see details in [Appendix E](#)):
  - Post-menopausal, defined as aged  $\geq 50$  years and amenorrhoeic for at least 12 months following cessation of all exogenous hormonal treatments
  - Women  $< 50$  years old who are considered as post-menopausal (amenorrhoeic for 12 months or more following cessation of all exogenous hormonal treatments) and who have luteinizing hormone (LH) and follicle-stimulating hormone (FSH) levels in the post-menopausal range for the institution
  - Documentation of irreversible surgical sterilisation by hysterectomy, bilateral oophorectomy or bilateral salpingectomy but not tubal ligation.
9. Male patients should be willing to use barrier contraception ie, condoms until 6 months after the last study drug is taken.

10. Patients are willing and able to comply with the protocol for the duration of the study including undergoing treatment and scheduled visits and examinations.

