## **Appendix E Acceptable Birth control Methods**

### **Osimertinib is regarded as a compound with medium/high foetal risk**

Patients of childbearing potential and their partners, who are sexually active, must agree to the use of 2 highly effective forms of contraception throughout their participation in the study and for 3 months (females) and 6 months (males) after last dose of study drug.

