#### **Acceptable non-hormonal birth control methods include:**

- True sexual abstinence. When this is in line with the preferred and usual lifestyle of the patient. [*Periodic abstinence (eg, calendar, ovulation, symptothermal, post-ovulation methods) and withdrawal are not acceptable methods of contraception*]. Abstinence must be for the total duration of the study and until 3 months (females) and 6 months (males) after discontinuation of study treatment.
- Vasectomised sexual partner plus male condom. With participant assurance that partner received post-vasectomy confirmation of azoospermia.
- Tubal occlusion plus male condom with spermicide
- Intrauterine device (IUD) plus male condom + spermicide. Provided coils are copper-banded.

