#### **Acceptable hormonal methods:**

- IUS Levonorgestrel Intra Uterine System (Mirena) + male condom with spermicide
- Medroxyprogesterone injections (Depo-provera) + male condom with spermicide.

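### Section 3.8 item 1 sets a looser contraception rule for women than Appendix E, the standard that inclusion criterion 8 cites

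*Protocol*

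**What the plan says.** **Section 3.8, item 1** applies to women of child-bearing potential from screening until 3 months after study treatment stops. It asks for reliable methods and gives a list of acceptable ones: true abstinence, then "tubal ligation, oral or transdermal contraceptives, copper-banded intra-uterine devices and vasectomised partner". A partner's condom is required only with hormonal methods. Spermicide is not mentioned and no number of methods is stated. The item also warns that hormonal contraceptives might become less effective.

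**Appendix E** rates osimertinib as medium/high foetal risk and says that sexually active patients of childbearing potential and their partners "must agree to the use of 2 highly effective forms of contraception throughout their participation in the study", continuing for 3 months after the last dose for women. Its non-hormonal entries, apart from abstinence, are:
- "Vasectomised sexual partner plus male condom"
- "Tubal occlusion plus male condom with spermicide"
- "Intrauterine device (IUD) plus male condom + spermicide. Provided coils are copper-banded"

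Its hormonal list has two entries: "IUS Levonorgestrel Intra Uterine System (Mirena) + male condom with spermicide", and medroxyprogesterone injection, also with condom and spermicide.

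**Section 3.1, criterion 8** requires adequate contraception and refers to Appendix E. Surgical evidence of non-child-bearing potential is limited to hysterectomy, "bilateral oophorectomy or bilateral salpingectomy but not tubal ligation".

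**Section 3.3** tells the investigator how entry is decided: "Determine patient eligibility. See Sections 3.1 and 3.2".

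**Pregnancy testing.** Criterion 8 requires a negative serum test before dosing. Section 4.1, Table 1, Table 3 and Section 5.2.1 accept either urine or blood.

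**The concern.** Two parts of one protocol give different contraception rules to the same women over the same post-treatment tail. Entry is judged against 3.1 and 3.2, so Appendix E reaches eligibility through criterion 8. Once a woman is on study, 3.8 and Appendix E both apply, and nothing says which prevails. Section 3.8 holds the restrictions for the treatment period and afterwards, so it is a natural place for a site to look when advising a patient. Item 1 does not refer to Appendix E, although item 3 of the same section does refer to Appendix G.

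The stake is foetal safety, and with it the patient's own treatment. If a woman on the weaker rule becomes pregnant, the foetus is exposed to osimertinib. Section 6.6.1 then requires osimertinib, her cancer treatment, to stop at once, and Section 3.10 lists pregnancy as a reason for withdrawal. There is also a compliance issue: Sections 3 and 3.4 allow no exception to eligibility, yet a woman using only what 3.8 accepts can fall short of what criterion 8 points to.

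**Working it through.** The plan gives no figure to reproduce. The check sets the two lists side by side and then works out how long the rule applies.

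**1. Method by method**

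| Entry in 3.8 item 1 | Added by 3.8 | Appendix E | Result |
|---|---|---|---|
| True abstinence | nothing | accepted alone | agrees |
| Tubal ligation (occlusion) | nothing | condom and spermicide | no condom, no spermicide |
| Copper IUD | nothing | condom and spermicide | no condom, no spermicide |
| Vasectomised partner | nothing | condom | no condom |
| Oral or transdermal hormonal | condom | not listed | outside the hormonal list |

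Counting oral or transdermal as one entry, 1 of 5 agrees, 3 of 5 lack the condom (2 of those 3 also lack spermicide), and 1 of 5 is not listed. Appendix E's own hormonal methods are not named in 3.8, but 3.8 introduces its list with the verb include, so it does not bar them.

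**2. Number of methods.** Appendix E requires two highly effective forms. Section 3.8 states no number. A condom is the only second method it asks for, and only with hormonal products.

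**3. Could another item fill the gap?** Section 3.8 item 2 requires condoms, but of male patients. It says nothing about the partners of female patients.

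**4. Tubal ligation.** Criterion 8 does not count it as sterilisation, so a ligated woman remains of child-bearing potential and needs contraception. Section 3.8 then names her ligation as an acceptable method and adds nothing to it. Appendix E adds condom and spermicide.

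**5. How long the rule runs** for a woman who completes the PK phase and does not enter continued access. Inputs:
- Screening to first dose: 2 to 28 days (Table 1).
- First fexofenadine dose to Treatment Period 2 Day 1: 3 to 7 days (Table 1 footnote; Section 7.2.1).
- Treatment Period 2 Day 1 to the last PK-phase osimertinib dose, nominally Day 41 and moving with the ±3-day window on Day 39: 40 ± 3, so 37 to 43 days.
- Three months after the last dose: taken as 91 days (assumption).

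Minimum: 2 + 3 + 37 + 91 = 133 days.
Maximum: 28 + 7 + 43 + 91 = 169 days.

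Counted from the first osimertinib dose only, the span is 37 + 91 = 128 to 43 + 91 = 134 days. Continued access lengthens both.

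**6. Pregnancy test.** A serum test satisfies every section. A urine-only test satisfies 4.1, Table 1, Table 3 and 5.2.1, but not criterion 8.

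**The case against.** The strongest reply is that Appendix E is not limited to entry. It covers the whole of participation and the 3 months afterwards, in mandatory terms. A correctly enrolled woman has therefore accepted the stricter rule for the period that 3.8 covers, and following Appendix E breaches nothing in 3.8. On this reading the remaining risk is a site that reads 3.8 in isolation. That is a fair account of how the error would arise, but it does not remove it: 3.8 gives a complete-looking list of acceptable methods, does not refer to Appendix E and states no precedence.

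A second reply is that 3.8 never says one method is enough, since it speaks of methods in the plural and of a list that includes certain items. Relying on ligation alone is indeed an inference, but a reasonable one. An open list can admit further methods; it does not attach a condom to a method already named as acceptable. By asking for a condom with hormonal methods only, 3.8 implies that none is needed with the rest. Reading Appendix E's lists as open also would not help, because the two-form rule and the condom pairings would still conflict with 3.8.

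Three narrower points have some force:
- Criterion 8 and 3.8 do agree that a ligated woman is of child-bearing potential. The conflict lies in the missing condom and spermicide, as with the copper IUD.
- The 133 to 169 days measure how long the rule runs, not osimertinib exposure; up to 28 + 7 = 35 of those days come before any osimertinib.
- Repeat pregnancy tests at screening, Day 1 of each period, Day 39 and follow-up (5.2.1) limit undetected exposure, though they do not prevent pregnancy.

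The serum and urine mismatch is a separate, smaller matter and is treated here as secondary.

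**Conclusion.** The concern holds. Section 3.8 item 1 is looser than Appendix E for four of its five entries and omits the two-form requirement. A sexually active woman of child-bearing potential who follows 3.8 as written can use less contraception than the protocol's mandatory standard. For a PK-phase completer without continued access the rule applies for about 133 to 169 days, taking 3 months as 91 days.

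The practical reach cannot be sized. The study plans about 24 patients, and the document does not say how many women would use these methods. Women who abstain or already use an Appendix E combination are not affected. The PK objectives and analysis are not affected either. It should be corrected because the rule protects against foetal exposure and the correction is simple. The serum versus urine inconsistency is also real, but minor.

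**What to change.** In Section 3.8 item 1, delete the list of methods and refer to Appendix E as the single governing list. Keep the condom sentence and the warning about hormonal methods. Once Appendix E governs, the condom sentence is compatible with its condom-plus-spermicide requirement; naming spermicide there as well would remove any doubt.

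Secondary change: either specify serum for the pre-dose eligibility test in Section 4.1, Table 1, Table 3 and Section 5.2.1, or amend criterion 8 to accept urine or serum.

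The cost is protocol wording, plus consent-form wording if the form repeats the 3.8 list. No visit or procedure is added. If serum is chosen, sites that would have used urine will need a blood test instead; Table 1 already schedules blood sampling at screening, but Table 4 carries no volume for a pregnancy test and would need a line. Amending criterion 8 avoids that.

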### **3.9 Discontinuation of investigational product**

Patients may be discontinued from IP in the following situations:

- Patient decision. The patient is at any time free to discontinue treatment, without prejudice to further treatment
- Adverse Event
- Severe non-compliance with the study protocol
- Worsened condition
- Disease progression
- The Investigator believes they are no longer deriving clinical benefit (continued access).
- Incorrectly enrolled patients

#### **3.9.1 Procedures for discontinuation of a patients from investigational product**

At any time, patients are free to discontinue IP or withdraw from the study (ie, IP and assessments – see Section [3.10](#)), without prejudice to further treatment. A patient that decides to discontinue IP will always be asked about the reason(s) and the presence of any AEs. If

possible, they will be seen and assessed by an Investigator(s). Adverse events will be followed up (See Section 6.3.2); and all study drugs should be returned by the patients.

In the PK phase, any patient discontinuing IP should be seen at 30 days ( $\pm 7$  days) after their last dose for the evaluations outlined in the study plan (see Table 1). After discontinuation of IP, the Investigator will perform the best possible observations, tests, and evaluations, as well as give appropriate medication and ensure all possible measures for the safety of the patient. In addition, they will record on the eCRF the date of discontinuation, the reasons, manifestation, and treatment at the time of discontinuation. If patients discontinue IP, the AstraZeneca monitor or its representative must be informed immediately. The patient should return all IP.

After discontinuation of the IP in the PK phase, all ongoing AEs or SAEs must be followed until resolution unless, in the Investigator's opinion, the condition is unlikely to resolve due to the patient's underlying disease, or the patient is lost to follow up (see Section 6.3). All new AEs and SAEs occurring during the 30 calendar days after the last dose of IP or immediately before initiation of any other cancer therapy, whichever occurs first, must be reported (all SAEs must be reported to AstraZeneca or its representative within 24 hours as described in Section 6.4) and followed to resolution as above. Patients should be contacted at least 30 days after discontinuing IP to collect and/or complete AE information and collect IP. Any untoward event occurring subsequent to the 30 day follow-up AE reporting period that the Investigator assesses as possibly related to the IP should also be reported as an AE.

At the end of the PK phase, patients may continue to receive IP as continued access and undergo follow-up as part of their normal routine clinical care. After discontinuation of the IP in continued access, patients should be followed for 30 days to follow-up any existing SAEs and monitor for any new SAEs that may be related to IP.

If a patient is withdrawn from study, see Section 3.10.

### **3.10 Criteria for withdrawal**

Patients will be withdrawn from the study for the following reasons:

- Screen failures (see Section 3.10.1)
- Voluntary withdrawal by the patient who is at any time free to discontinue their participation in the study, without prejudice to further treatment (see Section 3.10.2)
- Risk to patients as judged by the Investigator and/or AstraZeneca or its representative.
- Severe non-compliance to protocol as judged by the Investigator and/or AstraZeneca or its representative.

- Incorrectly enrolled patients, ie, the patient does not meet the required inclusion/exclusion criteria for the study.
- The patient becomes pregnant.
- Patient lost to follow-up.

### **3.10.1 Screen failures**

Screening failures are patients who do not fulfil the eligibility criteria for the study, and therefore must not be dosed. These patients should have the reason for study withdrawal recorded as 'Eligibility Criteria Not Fulfilled' (ie, patient does not meet the required inclusion criteria or meets an exclusion criterion). This reason for study withdrawal is only valid for screen failures (not dosed patients).

### **3.10.2 Withdrawal of the informed consent**

Patients are free to withdraw from the study at any time (IP and assessments), without prejudice to further treatment (withdrawal of consent). Patients may withdraw from any aspects of the optional genetics research (see Sections 3.1 and 5.6) at any time, without prejudice to further treatment and independent of any decision concerning participation in other aspects of the main study.

If a patient wishes to withdraw their consent to further participation in the study entirely this should be clearly documented in the patient notes and in the clinical study database. Patients will always be asked about the reasons for withdrawal of consent for and the presence of any AEs. If possible, they will be seen and assessed by an Investigator(s). Adverse events will be followed up (See Section 6.3.2); and all study drugs should be returned by the patients.

If a patient withdraws from participation in the study, then his/her E-code cannot be reused.

